4.5.2 Medical History

Medical history from the screening visit will be summarized by treatment group and overall. Medical history will be coded using the MedDRA version 19.0. The number and percentage of subjects experiencing at least one such diagnosis will be summarized by the MedDRA system organ class (SOC) and preferred term (PT) (Analysis population: ITT).

Summary (n, %) may be presented according to MedDRA groups for specific MH analyses (such as asthma, food allergy, allergic conjunctivitis, etc).

By-subject listings of medical history will be provided.

4.5.3 Prior and concomitant therapies

Start and stop dates of medications or medical and surgical procedures will be compared to the date of first dose of study drug to allow them to be classified as either Prior or Concomitant.

Medications or medical and surgical procedures that start and stop prior to the date of first dose of study drug will be classified as Prior. Prior medications that are taken from the date of screening to the date prior to randomization, regardless of start or stop, are also classified as Run-In Medications.

If start and/or stop dates of medications or medical and surgical procedures are missing or partial, the dates will be compared as far as possible with the date of first dose of study drug. Medications or medical and surgical procedures will be assumed to be Concomitant, unless there is clear evidence (through comparison of partial dates) to suggest that they started and stopped prior to the first dose of study treatment. If there is clear evidence to suggest that the medication or medical and surgical procedure started and stopped prior to the first dose of study drug, they will be assumed to be Prior.

Missing date information for prior and concomitant medications

For prior and concomitant medications, incomplete (i.e., partial missing) start dates and/or stop dates will be imputed. When the start date and the stop date are both incomplete for a subject, the start date will be imputed first.

Incomplete start date

The following rules will be applied to impute the missing numeric fields for an incomplete prior or concomitant medication start date. If the stop date is complete (or imputed) and the imputed start date is after the stop date, then the start date will be imputed using the stop date.

Missing Month and Day

- If the year of the incomplete start date is the same as the year of the first administration of the study drug, then the month and day of the first administration of the study drug will be assigned to the missing fields.
- If the year of the incomplete start date is before the year of the first administration of the study drug, *December 31* will be assigned to the missing fields.
- If the year of the incomplete start date is after the year of the first administration of the study drug, *January 1* will be assigned to the missing fields.

Missing Month Only

- If only the month is missing, then the day will be treated as missing and both the month and the day will be replaced according to the procedure above.

Missing Day Only

- If the month and year of the incomplete start date are the same as the month and year of the first administration of the study drug, then the day of the first administration of the study drug will be assigned to the missing day.
- If either the year of the incomplete start date is before the year of the date of the first administration of the study drug or if both years are the same but the month of the incomplete start date is before the month of the date of the first administration of the study drug, then the last day of the month will be assigned to the missing day.

- If either the year of the incomplete start date is after the year of the date of the first administration of the study drug or if both years are the same but the month of the incomplete start date is after the month of the date of the first administration of the study drug, then the first day of the month will be assigned to the missing day.

If the stop date is complete and the imputed start date as above is after the stop date, then the start date will be imputed by the stop date.

Incomplete stop date

The following rules will be applied to impute the missing numeric fields for an incomplete prior or concomitant medication stop date. If the date of the last administration of the study drug is missing, then replace it with the last visit date in the imputations described below. If the imputed stop date is before the start date (imputed or non-imputed start date), then the imputed stop date will be equal to the start date.

Missing Month and Day

- If the year of the incomplete stop date is the same as the year of the last administration of the study drug, then the month and day of the last administration of the study drug will be assigned to the missing fields.
- If the year of the incomplete stop date is before the year of the last administration of the study drug, *December 31* will be assigned to the missing fields.
- If the year of the incomplete stop date is after the year of the last administration of the study drug, *January 1* will be assigned to the missing fields.

Missing Month Only

- If only the month is missing, then the day will be treated as missing and both the month and the day will be replaced according to the above procedure.

Missing Day Only

- If the month and year of the incomplete stop date are the same as the month and year of the last administration of the study drug, then the day of the last administration of the study drug will be assigned to the missing day.
- If either the year of the incomplete stop date is before the year of the date of the last administration of the study drug or if both years are the same but the month of the incomplete stop date is before the month of the date of the last administration of the study drug, then the last day of the month will be assigned to the missing day.
- If either the year of the incomplete stop date is after the year of the date of the last administration of the study drug or if both years are the same but the month of the incomplete stop date is after the month of the date of the last administration of the study drug, then the first day of the month will be assigned to the missing day.

4.5.3.1 Prior and concomitant medications

Prior and concomitant medications will be coded using the World Health Organization Drug Dictionary (WHODD), version March 2016.

Prior and Concomitant medications will be summarized separately by Anatomical Therapeutic Chemical (ATC) level 2, level 3, and preferred name in frequency tables (Analysis population: ITT). Subjects with more than one medication in a given ATC level and preferred name will be counted only once in that category. The following summaries will be produced:

- Number and percentage of subjects who had Prior medications by ATC level 2, level 3, and preferred name
- Number and percentage of subjects who had Concomitant medications by ATC level 2, level 3, and preferred name
- Number and percentage of subjects who had medications during run-in period by ATC level 2, level 3, and preferred name

Number and percentage of subjects who had medications during treatment period by ATC level 2, level 3, and preferred name

A by-subject listing of all prior and concomitant medications will be provided.

4.5.3.2 Prior and concomitant medical and surgical procedures

Medical and surgical procedures will be coded using the MedDRA version 19.0.

Prior and Concomitant medical and surgical procedures will be summarized separately by SOC and PT in frequency tables (Analysis population: ITT). Subjects with more than one procedure in a given SOC and PT will be counted only once in that category. The following summaries will be produced:

- Number and percentage of subjects who had Prior medical/surgical procedures by SOC and PT
- Number and percentage of subjects who had Concomitant medical/surgical procedures by SOC and PT

A by-subject listing of all prior and concomitant medical and surgical procedures will be provided.

4.5.3.3 Rescue therapies

The number and percentage of subjects initiating use of rescue therapies will be summarized overall and by preferred name (for rescue medications) or preferred term (for rescue procedures) for all subjects in the ITT population. Rescue medication will be summarized by topical and systemic groups. Subjects with more than one rescue therapy in a given preferred name or preferred term will be counted only once in that category.

By-subject listings of all rescue therapies will be provided.

4.6 Treatment Compliance

Subject compliance with study treatment will be assessed via relative dose (%) of study drug. Refer to Section 4.8.1 for more analyses.

Study drug usage: Actual Dose (mg) of study drug at each planned dosing day is defined as

CCI

where: start volume in syringe = 1.0 mL.

Actual Total Dose (mg) is defined as the sum of the actual doses (mg) administered to a subject during a specified period.

Prescribed Total Dose (mg) is defined as the sum of the prescribed doses (mg) to a subject during a specified period.

Relative Dose (%) is defined as

CCI

The study drug compliance will be evaluated according to number of injections. Subjects with a compliance rate (number of actual injection / number of planned injection x 100) between 80% and 120% is considered as compliant with study drug during their participation in the study. Proportion of subjects considered as compliant with study drug will be summarized.

TCS usage: TCS are dispensed at screening, baseline, weeks 4, 8, 12, 16, 20, 24, 28, and returned at subsequent visit and weighted. Additional dispensation and weight may also occur at weeks 1 & 2, and/or unscheduled visits.

Actual Dose (g) at each planned dosing interval (one dispensation-return cycle) is defined as

CCI

In general, this will be considered as the monthly TCS usage. TCS dispensed at baseline, week 1 and 2 (returned at weeks 1, 2 and 4, respectively) will be summed up to get the TCS usage for the first month.

Actual Total Dose (g) of background TCS is defined as the sum of the actual doses (g) administered to a subject during a specific period (e.g., during the study treatment period). This information during the follow-up period should also be included. TCS usage will be presented by potency level and overall.

CCI

For missing TCS, the following rules will be followed:

- Dispensed weight: missing; returned weight: not missing
Impute the missing dispensed weight by the weight of another intact tube (entered by site).

- Dispensed weight: missing; returned weight: missing
The worst case scenario is that the subject has used the entire tube. Therefore, consider to use the content of the entire tube (45, 50, 15 or 30g depending on the actual TCS) instead of imputing the missing data. So the result of subtracting returned weight from dispensed weight is the content of the tube i.e. return weight imputed as 0.

- Dispensed weight: not missing; returned weight: missing
To apply the same way of imputation as above, using the total content of the tube as the weight of TCS used.

By-subject listings of study drug administration and compliance and TCS usage will be provided.

4.7 Efficacy Evaluation

Primary inference for efficacy analysis will be based on the ITT population at week 24.

The following efficacy endpoints will be analyzed at each visit up to week 24:

- Percent change from baseline in EASI
- Proportion of subjects achieving IGA success (defined as IGA 0 [clear] or 1 [almost clear])
- Percent change from baseline in weekly average of the peak pruritus NRS
- Proportion of subjects with an improvement of weekly average pruritus peak NRS ≥ 4
- Proportion of subjects with EASI-50, EASI-75 or EASI-90 (defined as achieving 50%, 75% or 90% reduction from baseline in EASI score)

All other efficacy endpoints (except above) will be analyzed at week 24 and summarized descriptively for the rest of visits.

The follow-up data for all efficacy endpoint will be summarized descriptively only.

Sensitivity analysis and subgroup analysis (where applicable) will be carried out for Week 24 only.

4.7.1 Analysis and Data Conventions

This study is designed to test for superiority. The null hypothesis is that there is no dose response effect for nemolizumab (10 mg, 30 mg, 90 mg) in percent change from baseline in EASI at week 24. The alternative hypothesis will be that there is a dose response.

4.7.1.1 Multi-center Studies

For the purpose of the summaries and analyses, the term ‘Center’ will be used to define each investigator site.

If at end the impact of the center(s) justified, the ad hoc analyses will be performed by including ‘Center’ as a main effect term in the model. In that case, the centers may be grouped by geographic regions (Europe, North America, Asia-Pacific). Evaluation of the consistency of treatment effects across geographic regions will be performed via subgroup analysis (see Section 4.7.1.6).

4.7.1.2 Adjustments for Covariates

The primary efficacy analysis will be adjusted for the following baseline covariates:

- Baseline IGA severity (the stratification factor)
- Baseline EASI

4.7.1.3 Handling of Missing Data

Use of rescue therapy: For the purpose of efficacy analysis, subjects receiving any rescue therapies will be considered as treatment failures. All efficacy data, except Observed Case (OC), will be set to missing after rescue medication is used. In OC analysis, observed data after subject has received rescue treatment will be included.

Diary data: If a subject has less than 4 diary entries in a week, the weekly prorated average scores will be set to missing.

The following methods will be used to impute the missing values:

Continuous endpoints: To impute the missing values for the primary analysis of continuous endpoints, Mixed-effect Model for Repeated Measures (MMRM) approach will be used for the primary and secondary endpoints (where applicable).

In addition, the following imputation approaches will be carried out as sensitivity analyses for primary and selected secondary endpoints to assess the robustness of findings. For sensitivity analyses, continuous endpoints will be analysed using analysis of covariance (ANCOVA) including terms of treatment group, baseline IGA severity (randomization strata), and the corresponding baseline value.

1. **Multiple imputation (MI) method under assumption missing at random (MAR):**

- a. Imputation phase: The missing data are filled in m times to generate m complete data sets. The selection of m depends on the required computing time. A reasonable range is 20 to 100 times, or may follow a rule of thumb that the number of imputations should be similar to the percentage of cases that are incomplete.
- b. Analysis phase: The m complete data sets are analyzed by using the same method as the corresponding primary analysis.

- c. Pooling phase: The results from the m complete data sets are combined for the inference.
2. **Last Observation Carried Forward (LOCF):** The last observed post-baseline value will be used to replace missing values for continuous variables. For questionnaire-based variables, LOCF will be applied to missing individual questions first, and the value of the total (or sub-scale) score will be derived based on the imputed individual questions.
3. **Worst Observation Carried Forward (WOCF):** The worst observed post-baseline value will be used to replace missing values for continuous variables. For questionnaire-based variables, WOCF will be applied to missing individual questions first, and the value of the total (or sub-scale) score will be derived based on the imputed individual questions.
4. **Observed Case (OC):** No data will be imputed. The observed values are used in analysis, including assessments post rescue medication.
5. **Pattern-mixture model under assumption missing not at random (MNAR), controlled-based pattern imputation:** refer to the 3 phases for MI-based imputation above. With controlled-based pattern imputation, only observations in placebo treatment group are used to derive the imputation model.

Binary endpoints:

All missing values will be treated as a Non-Responder for the binary endpoints. If a subject withdraws from the study, all assessment after withdrawal will be considered as Non-Responder.

LOCF, OC, MI and Pattern-Mixture Model under missing not at random assumption approaches will be used as sensitivity analysis to impute the missing values for the selected secondary endpoints as appropriate. For sensitivity analyses, binary endpoints will be analysed using **Cochran-Mantel-Haenszel (CMH)** test stratified by baseline IGA severity.

There will be no imputations for missing laboratory and vital sign data.

4.7.1.4 Multiple Comparisons/Multiplicity

Multiple comparison procedures-modeling (MCP-Mod, Bretz 2005) approach handles the multiplicity using a set of candidate dose-response models to test for a dose-response relationship via model-associated statistics.

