4.7.2 Primary Efficacy Endpoint

The primary variable for the assessment of efficacy is the percent change from baseline in EASI at week 24.

The primary endpoint will be analyzed using a MMRM approach, including terms of treatment group, and baseline IGA severity for ITT and PP populations. Visit will be fitted as a categorical variable, with the effect of treatment group and baseline IGA varying at each visit (i.e., interaction between treatment group and visit and interaction between baseline IGA and visit). The corresponding baseline values of the response variable will be included as a covariate in the model. An unstructured (UN) covariance matrix for repeated measures within a subject will be used to model the within-subject errors in the analysis, unless there are issues related to convergence. If the UN covariance matrix leads to non-convergence, then Akaike's information criterion (AIC) will be used to select the best covariance matrix among autoregressive, compound symmetric, and Toeplitz. The Kenward-Rogers adjustment will be used with restricted maximum likelihood (REML) to make proper statistical inferences. Denominator degrees of freedom will be estimated using approximation of Kenward-Rogers. A linear contrast will be used, within the MMRM framework, to estimate difference between each nemolizumab

dose regimen and placebo. LSmeans with 95% CI and the corresponding statistical p-value will be presented for the treatment difference between each nemolizumab dosing regimen and placebo at a given visit.

Other covariates may be explored and will be added into the model, if appropriate.

Dose Response Analysis: MCP-Mod approach will be applied using a set of candidate dose-response models (see table below) to test for a dose-response relationship via model-associated statistics. The analysis will be performed using the available R software package “MCPMod” or any other available software.

Linear	E _{max}	Sigmoid E _{max}
Linear	1. ED50=10mg 2. ED50=30mg	1. ED50=10mg, H (Hill)=1 2. ED50=10mg, H (Hill)=2 3. ED50=10mg, H (Hill)=3 4. ED50=15mg, H (Hill)=2 5. ED50=20mg, H (Hill)=4 6. ED50=30mg, H (Hill)=2

ED50=dose produces 50% of maximum effect

Sensitivity analysis: The robustness of the primary analysis will be investigated by performing the sensitivity analyses as described in 4.7.1.3.

Subgroup analysis: The homogeneity of the treatment effect for a number of important subgroups will be investigated as described in 4.7.1.6.

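### Does the SAP leave the test of its null hypothesis open because it never names the week-24 input to MCP-Mod?

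*SAP*

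**What the plan says.** Three parts of the SAP rest on MCP-Mod. Section 4.7.1 says: "The null hypothesis is that there is no dose response effect for nemolizumab (10 mg, 30 mg, 90 mg"), for percent change in EASI at week 24. Section 4.7.1.4 is one sentence, under which the MCP-Mod "approach handles the multiplicity using a set of candidate dose-response models to test for a dose-response relationship via model-associated statistics". Section 4.10 bases the power on it at one-sided 0.025 and points to 4.7.2 for the candidate curves.

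Section 4.7.2, on the primary endpoint, describes an MMRM with treatment, baseline IGA, visit interactions and the baseline value. Under the same heading follows a Dose Response Analysis by MCP-Mod with a table of candidates. On execution it says only "The analysis will be performed using the available R software package" MCPMod, or other software. Protocol 9.1.5.2.1, headed as the primary efficacy analysis, pairs the two in the same way.

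The surrounding rules speak of the primary analysis in general:

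- Covariates (4.7.1.2): "The primary efficacy analysis will be adjusted for the following baseline covariates", namely baseline IGA and baseline EASI.
- Missing data (4.7.1.3): "To impute the missing values for the primary analysis of continuous endpoints, Mixed-effect Model for Repeated Measures (MMRM) approach will be used". This rule covers secondary endpoints as well as the primary one.
- Rescue (4.7.1.3): "All efficacy data, except Observed Case (OC), will be set to missing after rescue medication is used".
- Robustness (4.7.2): "The robustness of the primary analysis will be investigated by performing the sensitivity analyses as described in 4.7.1.3". There, "For sensitivity analyses, continuous endpoints will be analysed using analysis of covariance (ANCOVA) including terms of treatment group", baseline IGA and the baseline value. Item 1b of the same section, however, has each multiply imputed data set analysed as in the matching primary analysis, and item 5 (control-based imputation) refers back to those phases.

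**The concern.** The test that carries the null hypothesis, the efficacy multiplicity control and the power is specified less fully than the MMRM beside it. No sentence names its week-24 input, 4.7.2 does not restate its level, and no sensitivity analysis is explicitly described as a rerun of it.

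Rescue is given for worsening AD and later data are blanked, so placebo may lose more week-24 values than the active arms. Contrasts on observed values would then compare a favourably selected placebo group with the doses and flatten the curve. MMRM means would use the rescued subjects' earlier visits. If both inputs complied with the SAP, two analysts could disagree on whether a dose response was shown, in a trial meant to choose doses for phase 3.

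**Working it through.** **1. The plan's own figure.** Inputs from SAP 4.10 and 4.7.2: n = 50 per arm, SD 45, maximum difference 30 points, one-sided 0.025, doses 0, 10, 30 and 90 mg, nine listed candidates. Emax with ED50 = 10 and sigmoid Emax with ED50 = 10 and Hill = 1 are the same curve, so eight are distinct.

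For Emax with ED50 = 10, d/(d+10) is 0, 0.5, 0.75, 0.9. Scaled to 30 at 90 mg, the differences from placebo are 0, 16.67, 25, 30, with mean 17.92. The deviations are −17.92, −1.25, 7.08, 12.08, and the root of their sum of squares is 22.78.

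Non-centrality = 22.78 × √50 / 45 = 3.58. With a critical value of about 2.25 (multivariate t, 196 df), the matching contrast alone has power Φ(3.58 − 2.25) = 0.908. Taking the maximum over all candidates raises this to 92.8%. Across the candidates the range is 92.8% to 98.3%, so at least 90% reproduces when the 30 points are reached at 90 mg. With 45, 40 or 35 evaluable per arm, the minimum is about 90%, 86% or 81%.

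**2. What the input choice does.** The documents give no rescue rate, dropout rate or visit correlation, so these are assumed. Settings: 1,500 trials per scenario, eight post-baseline visits, true curve Emax with ED50 = 10, equal between-visit correlation of 0.5 or 0.8, monotone loss. MCP-Mod was run on MMRM week-24 means with their covariance, and on an ANCOVA of observed week-24 values. Each cell gives the result for correlation 0.5 / 0.8.

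| True 90 mg difference | Missing at week 24 | Significant, MMRM input (%) | Significant, observed input (%) | Verdicts differ (%) |
|---|---|---|---|---|
| 30 | 5%, random | 92.1 / 92.0 | 92.0 / 91.3 | 1.7 / 1.8 |
| 30 | 10%, random | 91.7 / 91.7 | 90.3 / 89.4 | 3.2 / 3.7 |
| 30 | 20%, random | 87.6 / 90.6 | 85.5 / 84.3 | 5.7 / 8.1 |
| 30 | 28–29%, response-dependent | 83.7 / 89.9 | 76.8 / 77.7 | 10.5 / 14.8 |
| 30 | 43–45%, response-dependent | 74.3 / 85.0 | 62.9 / 66.3 | 15.0 / 22.3 |
| 0 | 10%, random | 2.1 / 2.5 | 2.2 / 2.4 | 0.7 / 1.6 |
| 0 | 33–34%, response-dependent | 2.5 / 2.7 | 2.3 / 2.3 | 2.0 / 3.5 |

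With a true difference of 20 points, disagreement runs from 4% to 25% over the same non-null scenarios.

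Most disagreements are trials that only the MMRM input declares positive. At 20% random loss and correlation 0.8, the net gap is 90.6 − 84.3 = 6.3 points and total disagreement is 8.1%. So (8.1 + 6.3)/2 = 7.2% are positive on MMRM only and 0.9% on observed values only.

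A second simulation triggers rescue when EASI is worse than baseline and uses unadjusted observed values as comparator. It points the same way. Its heaviest rescue level (Emax with ED50 = 10, correlation 0.85 between adjacent visits) gives power of 87.1% on MMRM input and 76.0% on observed values, with verdicts differing in 12.9%.

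**3. Which input the text supports.** The MMRM is the only primary model that 4.7.2 writes out for week-24 treatment effects. The missing-data rule names it, and it contains the covariates that 4.7.1.2 requires. The SAP's one observed-value analysis is Observed Case, a sensitivity analysis that keeps post-rescue data. Observed values with post-rescue data removed match neither description.

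**4. The level.** The default in SAP 4.2 is two-sided 5%, and 0.05/2 = 0.025 in the direction of benefit, which is the level in 4.10. The two do not conflict in practice.

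**5. The sensitivity analyses.** Contrast coefficients sum to zero, so each MCP-Mod numerator is a weighted sum of the three dose-minus-placebo differences. For Emax with ED50 = 10 the weights are −1.25/22.78 = −0.055, 7.08/22.78 = 0.311 and 12.08/22.78 = 0.531 for 10, 30 and 90 mg. Check: −0.055 × 16.67 + 0.311 × 25 + 0.531 × 30 = 22.8. An ANCOVA by treatment group under each missing-data assumption therefore yields the quantities that drive MCP-Mod.

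**The case for a change.** The strongest opposing case is that a SAP exists to remove such choices, and Protocol 9.1 promises a detailed technical description of the procedures. The natural reading is still an inference, and an analyst running contrasts on week-24 values would not contradict an explicit sentence. The choice can matter: under heavy response-dependent loss the verdict changes in more than one trial in ten. Item 1b and the ANCOVA sentence in 4.7.1.3 also pull in different directions, and neither mentions MCP-Mod.

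What stands is that the input is unstated, that 4.7.2 does not repeat the level, and that 4.7.1.3 does not settle whether MCP-Mod is rerun. One sentence would have been tidier.

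What does not stand is the claim that MCP-Mod has no missing-data rule, covariates or robustness checks. The rules are written for the primary analysis and MCP-Mod sits inside it. The sensitivity ANCOVA carries baseline IGA and the baseline value too. Item 1b, and item 5 through it, can be read as repeating the primary method on imputed data. Nor does the treatment-failure argument favour one input. The MMRM also blanks post-rescue data and does not score rescued subjects as failures, so choosing it leaves that tension in 4.7.1.3 where it was. Finally, the power gap is not a loss under the plan as written, because the weaker comparator is not an analysis that the SAP specifies.

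**Conclusion.** This is missing detail that a competent analyst fills sensibly: the ITT MMRM week-24 adjusted means and their covariance, tested at one-sided 0.025. With that reading the design keeps its stated power when data are complete, and no written rule gives a wrong result. Explicit MCP-Mod reruns, or labels marking other p-values as nominal, would be additions rather than corrections.

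If observed values were used instead, the verdict would differ in roughly 2% to 8% of trials at 5% to 20% random loss with a 30-point effect. It would differ in 11% to 15% at 28–29% response-dependent loss, and in up to 25% with heavier loss and a 20-point effect. All of this rests on assumed missing-data rates and correlations, since the documents give none. Neither input inflates type I error in the null scenarios run (2.1% to 2.7%). For a phase 2 dose-ranging trial, no change to the plan follows.
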